2.2.5. Within 2-3 days prior to chemotherapy

- Complete physical examination including vital sign measurements, weight and ECOG assessment should be conducted within 3 days prior to treatment. This can be performed by home oncologist if patient decides to undergo systemic therapy at home.
- Serum beta-HCG on all females of child bearing potential or urine pregnancy test within 2 days prior to treatment.

2.2.6. On Study within 1 week of surgical treatment:

- Physical examination including vital sign measurements, weight and ECOG assessment.
- Laboratory evaluation: CBC, platelets, Chem-20 (Sodium (Na), Potassium (K), Chloride (Cl), total CO₂ (bicarbonate), Creatinine, Glucose, Urea nitrogen (BUN), Albumin, Calcium total, Magnesium total (Mg), Inorganic Phosphorus, Alkaline Phosphatase, ALT/GPT, AST/GOT, Total Bilirubin, Direct Bilirubin, LD, Total Protein, total CK, Uric acid, PT/PTT & INR, Urinalysis.
- Base line tumor markers, Prealbumin and Ferritin.

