- Patients who enroll and are willing to have tissue collected for research purposes will be enrolled on protocol 09-C-0079.
- All patients found eligible will undergo staging laparoscopy with peritoneal lavage prior to randomization.
- Patients will be randomized following staging laparoscopy and after the results of the peritoneal washings are available.
- Stratification will adjust for site of metastases (liver, peritoneal and lung), disease-free interval (DFI), and previous systemic therapy for gastric metastases. Note: positive peritoneal washings will be stratified as peritoneal disease.
- Patients randomized to the GYMS approach and who have peritoneal disease will undergo, as an integral part of their treatment, complete peritonectomy and peritoneal perfusion (CHPP).
- Patients who present with intrabdominal disease without peritoneal involvement will undergo CHPP with limited peritonectomy as described in section 3.2.6
- All patients randomized to the GYMS arm will undergo gastrectomy, modified D2 lymph node dissection and/or appropriate metastasectomy followed by systemic therapy.
- *H. pylori* infection will be tested and treated following the recommendations of the American College of Gastroenterology guideline on the management of *H. pylori* infection⁷⁵ (Appendix 2). This treatment should not delay surgery.
- Patients randomized to the systemic therapy arm (SA) will receive systemic therapy preferably by their home medical oncologist or by the NCI Medical Oncology Branch.
- Systemic therapy: Since there is no definitive standard of care in metastatic gastric cancer and oxaliplatin and/or irinotecan were shown in phase III trials⁷⁶ to be equally effective to other common regimens in gastric cancer, patients will receive the FOLFOXIRI regimen as described by Masi et al from the GONO group⁷⁷.
- Patients in the SA arm who develop metastases synchronous to the primary gastric cancer will be eligible for palliative gastrectomy for pain, bleeding, obstruction and/or if deemed in the best interests of the patients.
- Palliative gastrectomy will include tumor resection (R0 when possible) and a bypass. As per standard of care, no adjacent organ resection (with the exception of obstructing lesions) will be performed.

- During follow up, all patients will undergo H&P laboratory evaluation and imaging studies and tumor markers as indicated. The timing of all follow up evaluations will be based on the date of randomization.

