3.1. Staging Laparoscopy

3.1.1. Patients who meet eligibility criteria will be taken to the operating room for staging laparoscopy and peritoneal washings. At laparoscopy biopsies of the peritoneum will be done and used later to confirm status of peritoneal disease (not as a part of the staging procedure but as part of the study).

- Any suspicious lesions that might preclude resection to NED will be biopsied as well.
- Liver ultrasound to confirm axial imaging findings will be done.
- Randomization and stratification will be done after laparoscopy and only after the results of the peritoneal washings are known (within one week of laparoscopy).

3.1.2. Patients will then be randomized to receive gastrectomy and/or metastasectomy plus systemic therapy (GYMS arm) or systemic therapy alone (SA arm).

- Patients randomized to receive the standard of care (SA arm) will receive systemic therapy (as described in Section 3.5). **Note:** Patients may undergo palliative gastrectomy if indicated but must begin chemotherapy within 6 weeks of gastrectomy (8 weeks following randomization).
- Patients randomized to receive gastrectomy and/or metastasectomy plus systemic therapy (GYMS arm) will be taken to the operating room within 1-2 weeks of randomization (as soon as feasible). Patients may undergo surgery only at the NCI. Subsequently, patients will receive systemic therapy within 4 to 16 weeks after surgery and/or when fully recovered from surgery. Patients who do not recover within 16 weeks will be taken off treatment and followed for survival. (**Note:** patients who undergo thoracotomy for pulmonary metastases must be able to receive systemic therapy within 24 weeks of their initial surgery.) This is an intent-to-treat phase III trial.

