3.5. Systemic Chemotherapy Therapy

3.5.1. Guidelines

Patients who randomize to receive systemic chemotherapy alone (SA) will begin treatment within 14 days of randomization; patients who undergo palliative gastrectomy will begin chemotherapy within 6-8 weeks of randomization. Patients who randomize to surgery plus chemotherapy (GYMS) will begin treatment approximately 6-8 weeks following surgery (24 weeks for patients requiring sequential thoracic and abdominal surgery). **Note:** patients must meet eligibility requirements prior to beginning chemotherapy. Patients who do not recover from the surgical procedure within the stated timeframe will be removed from treatment and followed for survival.

Systemic therapy may be administered by the patient's local oncologist in collaboration with the PI or at the NCI by the Medical Oncology Branch. Systemic therapy will follow the guidelines for the FOLFOXIRI regimen⁷⁷. Chemotherapy and supportive care will be administered in accordance with each institution's policies for the administration of chemotherapeutic agents.

During treatment, the treating oncologist will be asked to fax the following information (Appendix 8) to the research nurse (noted below) at the conclusion of every other cycle (4 weeks):

- chemotherapy administration sheets including dose reductions and reason for dose reduction
- laboratory test results
- other clinically relevant information

The patient will be asked to maintain a diary to be faxed to the research nurse every 4 weeks:

[name] RN
[contact]

All systemic chemotherapy will be administered based on actual body weight if within 20% above or below the ideal body weight. If actual weight is not within 20% of ideal body weight, then ideal body weight will be used to calculate systemic chemotherapy doses.

Ideal body weight will be calculated based upon the following formula:

$$\begin{aligned} \text{IBW (male, in kg)} &= \{(\text{Height in inches} - 60 \} \times 2.3 \} + 50 \\ \text{IBW (female, in kg)} &= \{(\text{Height in inches} - 60 \} \times 2.3 \} + 45.5 \end{aligned}$$

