3.5.3. Treatment Modifications FOLFOXIRI

Treatment will be continued for up to 12 cycles (4 cycles = 1 course) unless one of the following events occur: disease progression, unacceptable adverse effects, or withdrawal of patient consent. Dose modification will be based on toxicity profiles and adverse effects based upon the National Cancer Institute Common Terminology Criteria for Adverse Events (CTCAE version 3.0).

The dose levels for oxaliplatin, irinotecan, leucovorin and 5-FU are noted above; the dose modification table is attached as Appendix 4.

NOTE: Patients for whom peripheral neuropathy would pose significant hardship (e.g., musicians, jewelers, dentists) may receive the standard FOLFIRI regimen as noted below.

FOLFIRI			
Agent	Starting Dose	Dose level -1 (25% reduction)	Dose level -2 - 50% reduction
Irinotecan	180 mg/ m ² IV	150 / m ² IV	120 /m ² IV
Leucovorin	200 mg/m ² IV	200 m ² IV	200 mg/m ² IV
5-FU bolus	400 mg/m ² IV	320 mg/m ² IV	240 mg/m ² IV
5-FU infusion (over 46 hours)	2400 mg/m ² CIV	2000 mg/m ² CIV	1600 mg/m ² CIV

Day 1: Irinotecan will be administered IV over 90 minutes followed by leucovorin IV over 2 hours followed by 5-FU bolus injection, followed by 5-FU given via continuous infusion (CIV) over 46 hours. Dose reductions will follow appendix 4; all evaluations will follow the same schedule as outlined for FOLFOXIRI.

3.6. Treatment Evaluation During Chemotherapy:

- Laboratory evaluation weekly or according to the standards of the treating physician, to include: CBC with differential and Chem 20: (Sodium (Na), Potassium (K), Chloride (Cl), Total CO₂ (bicarbonate), Creatinine, Glucose, Urea nitrogen (BUN), Albumin, Calcium total, Magnesium total (Mg), Inorganic Phosphorus, Alkaline Phosphatase, ALT/GPT, AST/GOT, Total Bilirubin, Direct Bilirubin, LD, Total Protein, Total CK, Uric Acid).
- Physical examination and toxicity assessment every 2 weeks or according to the standards of the treating physician

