7.2. Routine Data Reporting

7.2.1. Following randomization, all adverse events will be described in the source documents, reviewed by the designated research nurse, and captured in C3D.

- All chemotherapy dose reductions and the reason for the reduction will be captured in C3D
- During the follow up period (more than 30 days following the last treatment), only those events that are serious, unexpected, and related to the treatment will be captured in C3D.

7.2.2. Laboratory events will be captured as follows:

- During hospitalization for surgical resection, only the admission labs, first morning labs drawn after 4am, and labs that support the diagnosis of a reportable event will be uploaded into C3D.
- During systemic chemotherapy regimen, for laboratory values obtained at sites other than the NIH Clinical Center: only the following values (highest grade per cycle) will be captured in C3D:
 - Hemoglobin, total white blood cell count, absolute neutrophil count, platelet count
 - PTT, PT or INR
 - Creatinine, ALT, AST, Bilirubin (total and direct),
 - Any unexpected laboratory abnormality \geq grade 2 possibly, probably or definitely related to the research

7.3. Exclusions to Routine Data Reporting:

The following Adverse Events will be captured only in the source documents and will not be reported in C3D

7.3.1. For the duration of the study:

- Laboratory values that do not support the diagnosis of a reportable event
- All grade 1 events

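### Non-NIH laboratory toxicity during chemotherapy is captured from a short list, and a home-care preference written for SA alone could make that gap differ by arm

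*Combined protocol and SAP*

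**What the plan says.** Two statements cover where chemotherapy is given. Section 3 (Study Implementation, Experimental Design) says "Patients randomized to the systemic therapy arm (SA) will receive systemic therapy preferably by their home medical oncologist", with the NCI Medical Oncology Branch as the alternative. Nothing equivalent is written for GYMS. Section 3.5.1, which governs chemotherapy in both arms, states no preference: "Systemic therapy may be administered by the patient's local oncologist in collaboration with the PI or at the NCI by the Medical Oncology Branch". Section 3.1.2 ties surgery to one place ("Patients may undergo surgery only at the NCI"), but that rule does not reach chemotherapy.

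Laboratory capture during chemotherapy depends on site. Section 7.2.2 sets the limit "for laboratory values obtained at sites other than the NIH Clinical Center: only the following values (highest grade per cycle") and then lists hemoglobin, white cells, neutrophils, platelets, PT/PTT/INR, creatinine, ALT, AST, total and direct bilirubin. It adds unexpected abnormalities of at least "grade 2 possibly, probably or definitely related to the research". No list is given for NIH values in this period.

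Section 7.2.1 asks for all adverse events after randomization, and all dose reductions with reasons, wherever the patient is treated. The exclusions in Section 7.3 apply at every site. Section 5.4 compares toxicity between arms by type and maximal grade and does not mention place of care.

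**The concern.** A capture rule that depends on site does no harm to a randomized comparison while sites are balanced between arms. The SA-only preference gives a reason to doubt that balance. GYMS patients are also in post-operative follow-up at 4 to 6 weeks (Section 3.4.4), not long before chemotherapy, and some may stay at the NCI for it. In that case the same laboratory toxicity is more likely to be entered for a GYMS patient than for an SA patient, and part of any difference in Section 5.4 would be an artefact of recording.

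The values exposed are ones that the protocol itself expects to move. Section 8.3.2 names hypocalcemia with 5-FU and leucovorin, and Section 8.4.2 names electrolyte imbalance after irinotecan diarrhea. Because they are named, Section 7.1.3 would not class them as unexpected, so the last item on the short list does not bring them back. The comparison also has an early use: until 68 patients are randomized, Section 5.5 has the monitoring board look at toxicity and adverse events only.

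**Working it through.** **The plan's own figure.** Nothing in the plan quantifies place of care. Its one relevant calculation, 121 deaths, reproduces: 4 × (1.960 + 0.842)² / (ln 1.667)² = 31.4 / 0.261 = 120.3, rounded up to 121. It rests on survival alone, so laboratory capture does not enter it.

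**What the short list leaves out.** Section 3.6 lists 20 Chem-20 analytes. Section 7.2.2 keeps 5 of them (creatinine, ALT, AST, total and direct bilirubin), so 20 − 5 = 15 are off the list, including sodium, potassium, calcium and magnesium.

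**What survives the exclusions that apply everywhere.** Section 7.3.1 drops grade 1 events and laboratory values that do not support a reportable event. Section 7.3.4 drops grade 1 and 2 events listed in a package insert, and listed grade 3 events without hospitalization. For listed, expected chemistry toxicity, this leaves grade 4 events and grade 3 events that need hospitalization. On a literal reading of Section 7.2.2, these are entered for NIH patients but not for others.

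**Size.** Let p be the true rate of such toxicity per patient, equal in both arms; h the share of an arm treated at home; and c the fraction of home events that still reach the database. Capture at the NIH is taken as complete.

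- Recorded rate = p × [1 − h × (1 − c)]
- False difference (GYMS minus SA) = p × (1 − c) × (h_SA − h_GYMS)

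The documents give none of p, h or c. All values below are assumptions.

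| Home share SA v GYMS | c | p = 10% | p = 30% |
|---|---|---|---|
| 80% v 80% | any | 0 | 0 |
| 80% v 60% | 0.5 | 0.10 × 0.5 × 0.2 = 1 point | 3 points |
| 80% v 60% | 0 | 0.10 × 1 × 0.2 = 2 points | 6 points |
| 80% v 40% | 0.5 | 0.10 × 0.5 × 0.4 = 2 points | 6 points |
| 80% v 40% | 0 | 0.10 × 1 × 0.4 = 4 points | 12 points |

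With 68 per arm and a two-sided 0.05 pooled two-proportion test, the chance of a false positive runs from 0.056 to 0.072 in the second row and from 0.220 to 0.578 in the last. These are normal approximations and are rough where counts are small (a recorded rate of 2% is 68 × 0.02 = 1.4 patients).

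The difference is proportional to p, and 10% to 30% may be too high. Section 1.2 reports no grade 4 non-hematologic toxicity in the phase II studies of this regimen. At an assumed p of 2%, the last row becomes 0.02 × 1 × 0.4 = 0.8 points.

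**The case against.** The strongest reply is that the documents do not tie place of care to arm. Section 3.5.1 allows either place in both arms. Section 2.2.5 leaves it to the patient ("This can be performed by home oncologist if patient decides to undergo systemic therapy at home"). Section 2.3 has the referring oncologist, or the NCI for patients treated there, notified at consent, so the intended place is often known before allocation. This stands. A reader might infer that place of care does differ by arm; the text supports only that it could.

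Second, Section 7.2.1 captures adverse events at any site, and Section 7.1.1 counts clinically significant laboratory abnormalities as adverse events. If that route works in practice, c is near 1 and the bias near zero. This stands in part. Section 7.2.2 is written as the rule for laboratory events and says that only the listed values are entered, so the two provisions pull against each other and c cannot be fixed from the text.

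Third, the list holds the main hematologic, renal and hepatic measures, and clinical toxicities such as diarrhea and neuropathy do not depend on it. This stands: the exposed part is narrow.

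Three further readings are tempting and not supported:

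- *That SA will look less toxic overall.* That direction holds only for off-list chemistry during chemotherapy, and only if SA has the larger home share. Section 7.3.2 omits grade 3 and 4 events that resolve within 72 hours of surgery, which mainly lowers recorded GYMS toxicity.
- *That a large relative excess can be stated.* With p = 15%, c = 0 and shares of 80% v 50%, the recorded rates are 0.15 × 0.20 = 3.0% and 0.15 × 0.50 = 7.5%, a 2.5-fold ratio. Every input is invented.
- *That the dosing objective in Section 1.1.2 is biased by the short list.* All dose reductions and reasons are captured at any site, from administration sheets that the treating oncologist sends in. Local practice could affect dosing if home shares differ, but that is not a capture problem, and nothing in the documents shows it.

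**Conclusion.** The concern holds in a limited form. The plan has a site-dependent capture rule for laboratory toxicity, a place-of-care preference written for one arm only, and a between-arm comparison that takes account of neither. Together they can under-record expected off-list chemistry toxicity in SA. This needs three conditions: a larger home share in SA than in GYMS, events that survive Section 7.3, and home events that do not arrive through general adverse event reporting. None of the three can be measured from the documents. Under the assumed inputs the false difference runs from 0 with equal home shares to 12 percentage points at the extreme, and it stays below 1 point if the surviving toxicity is as rare as 2%. Overall survival, the 121 deaths and the 136 patients are unaffected. The point is worth acting on because the remedy is small and removes the dependence on site from what is compared.

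**What to change.** 1. In Sections 5.4 and 7.2.2, state that the between-arm comparison of laboratory toxicity during chemotherapy uses the Section 7.2.2 list, highest grade per cycle, for NIH and non-NIH patients alike.
2. Reconcile Section 3 with Section 3.5.1 so that one statement on place of chemotherapy covers both arms. Which arrangement is adopted is for the sponsor.
3. Report place of chemotherapy (home or NCI) by arm beside the toxicity tables.

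The cost is a few sentences of protocol text and one descriptive table row. Some NIH laboratory values drop out of the between-arm comparison but stay available for safety review. A common list does not equalize how often patients are tested: Section 3.6 allows "Physical examination and toxicity assessment every 2 weeks or according to the standards of the treating physician" and gives the same latitude for laboratory tests. Reporting place by arm lets a reader judge whether that matters.

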3.1. Staging Laparoscopy

3.1.1. Patients who meet eligibility criteria will be taken to the operating room for staging laparoscopy and peritoneal washings. At laparoscopy biopsies of the peritoneum will be done and used later to confirm status of peritoneal disease (not as a part of the staging procedure but as part of the study).

- Any suspicious lesions that might preclude resection to NED will be biopsied as well.
- Liver ultrasound to confirm axial imaging findings will be done.
- Randomization and stratification will be done after laparoscopy and only after the results of the peritoneal washings are known (within one week of laparoscopy).

3.1.2. Patients will then be randomized to receive gastrectomy and/or metastasectomy plus systemic therapy (GYMS arm) or systemic therapy alone (SA arm).

- Patients randomized to receive the standard of care (SA arm) will receive systemic therapy (as described in Section 3.5). **Note:** Patients may undergo palliative gastrectomy if indicated but must begin chemotherapy within 6 weeks of gastrectomy (8 weeks following randomization).
- Patients randomized to receive gastrectomy and/or metastasectomy plus systemic therapy (GYMS arm) will be taken to the operating room within 1-2 weeks of randomization (as soon as feasible). Patients may undergo surgery only at the NCI. Subsequently, patients will receive systemic therapy within 4 to 16 weeks after surgery and/or when fully recovered from surgery. Patients who do not recover within 16 weeks will be taken off treatment and followed for survival. (**Note:** patients who undergo thoracotomy for pulmonary metastases must be able to receive systemic therapy within 24 weeks of their initial surgery.) This is an intent-to-treat phase III trial.

3.2. Gastrectomy, Metastasectomy, Peritonectomy and Intraperitoneal Therapy

Surgical Guidelines:

Note: The following guidelines are for the purpose of promoting consistency in the surgical procedure, and peri-operative care where possible. Physician discretion will be exercised as necessary to ensure that the specific needs of the patient are met. Details pertaining to surgical and perioperative management will be recorded in the patient medical record but will not be captured on the CRFs.

3.2.1. Preoperative Patient Management

- Patients will receive standard preoperative care as appropriate to the planned surgical intervention and the patient's underlying health status which may include:
 - The day prior to surgery: anti-embolism stockings (TEDS), Sequential Compression Devices (SCDS), incentive spirometry and appropriate bowel preparation regimen
 - The night before operation: Hibiclens® shower

Note: For patients undergoing hepatic resection, no anticoagulation will be given prior to operation.

3.2.2. Patient Management in the Operating Room:

- Patients will receive broad spectrum antibiotics in the recovery room before moving into the operating theater.
- Epidural catheters should be considered in all patients. Decisions will be made by the anesthesiologist and the operating surgeon in full collaboration.
- TEDS will be placed and SCDs will be “on” before induction of anesthesia.
- A central venous line, arterial line, and large bore catheters will be placed if blood loss is anticipated to be >500cc.
- In cases where liver resection is anticipated, fluid administration will be tightly coordinated with the operating surgeon. Before the liver parenchyma is transected administered crystalloids should be limited to <500ml when possible. During parenchymal transection the CVP should be kept under 4 and preferably at 0-1 using Trendelenburg position and vasodilators; urine output of 25 cc per hour will be considered sufficient.

3.2.3. Choice of Gastric Resection:

General Guidelines:

- The overall goal for surgical therapy is to render the patient NED and to obtain negative margins whenever technically feasible.
- All patients will receive an intraoperative ultrasound of the liver regardless of the preoperative imaging or laparoscopic ultrasound to determine if hepatic metastases exist even if preoperative imaging fails to show evidence of disease.
- Hand sewn anastomosis with PDS and a G-J tube placement for patients undergoing CHPP and gastrectomy will be preferred.
- A resection of surrounding organs will be allowed if the operating surgeon observes local invasion.
- The drainage procedure after gastric resections will consist of either a Billroth II or preferably, Roux-en-Y gastrojejunostomy when possible.

Type of resection

- Lesions of the gastric body or antrum: a “radical subtotal gastrectomy” will be performed: this will include an approximate 70-90% distal gastrectomy, and if technically feasible, ligation of the right gastric, right gastroepiploic, and left gastric arteries at their origin with removal of associated lymphoid tissues. The lesser and greater omentum will be removed if considered resectable.

- Proximal lesions: a total gastrectomy with 2-4 cm esophageal margins will be done when possible.
- Lesions of the cardia or fundus: a total gastrectomy will be performed where possible. Tumors extending < 4 cm into the esophagus will also be resected through the abdominal incision with the intention of gaining 2-4 cm negative margins on the esophagus.
- Distal lesions: a proximal subtotal gastrectomy (as opposed to total gastrectomy) with high ligation of the left gastric artery, removal of the gastrosplenic ligament, lesser omentum and surrounding lymphoid tissue will be done when possible

3.2.4. Lymph node dissection:

- Perigastric lymph nodes (stations 1, 3 and 5) and greater curvature lymph nodes (stations 2, 4 and 6) are grouped as N1 (D1 range); the nodes around the left gastric artery (station 7), common hepatic artery (station 8), celiac artery (station 9) and splenic artery (stations 10 and 11) are grouped as N2 (D2 range). More distant nodes such as para-aortic nodes (N3 and N4) are regarded as distant disease (M1).
- All visible perigastric lymph nodes will be removed along with technically feasible resections of lymph nodes along the following named arteries: 1) Right Cardiac, 2) Left Cardiac, 3) Left Gastric, 4) Celiac, 5) Splenic Artery, 6) Hepatic Artery, 7) Suprapyloric, 8) Infrapyloric, 9) and low paraesophageal according to the extent of gastrectomy.
- A modified D2 lymph node resection will be carried out to include removal of the omental bursa along with the posterior leaf of the transverse mesocolon, anterior leaf covering the pancreas, and lymph node stations 1-11 without obligatory splenectomy or distal pancreatectomy.
- The extent of a D2 resection will be determined by the operating surgeon depending on tumor characteristics and whether nodal regions can be accessed safely while sparing the spleen and pancreas. However, if the tumor is adherent to the spleen or invading the gastrosplenic ligament, a splenectomy will be performed

Note: Patients at risk for splenectomy (proximal T3-T4 lesions) may receive triple vaccination (Pneumococcal, Meningococcal, *Haemophilus influenzae*) prior to surgery.

3.2.5. Hepatic metastasectomy:

- Intraoperative ultrasound will be performed on all patients to detect disease not witnessed on preoperative imaging. Unexpected findings will be recorded in the patients chart.
- The goal of hepatic metastasectomy is to render the patient NED with at least 1 cm negative margins when possible.
- The preferred modality of hepatic metastasectomy is anatomical segmental resection. For single lesions, when possible, segmentectomy should be performed. For more than a single isolated lesion, a sectorectomy or partial hepatectomy should be performed if feasible. In all cases, the surgeon should strive to obtain negative margins.

- A non-anatomic wedge resection shall be performed only for small superficial lesions deemed resectable to negative margins by intra-operative ultrasound and preoperative imaging.
- In selected cases, intraoperative RFA and/or microwave ablation may be used at the discretion of the operating surgeons if deemed in the best interests of the patient.
- Portal vein ligation/embolization should be considered in selected patients to preserve post-operative liver function.
- A formal hepatic lobectomy will be done for large lesions spanning more than two sectors, or multiple lesions within a single hepatic lobe.
- In all cases of hepatic gastric metastasis undergoing liver resection, the surgeon should perform portal and hepatic artery lymph node dissection whenever possible.

3.2.6. Peritoneal metastasectomy (cytoreductive surgery):

- If there is evidence that the extent of disease is beyond the ability to be debulked such that the largest residual tumor nodule is less than or equal to 0.5 cm, patients will be considered ineligible and removed from treatment.
- For patients with primary peritoneal metastases (small disease load; P0-P2 disease) without massive ascites or intestinal obstruction, all visible disease will be resected if technically feasible.
- Complete peritonectomy for patients with peritoneal disease includes the following: the right and left sub-diaphragmatic peritoneum, the falciform ligament, lesser and large omentum, anterior, right and left abdominal wall down to the paracolic gutters and the pelvic peritoneum.
- Partial (limited) peritonectomy for patients with intra-abdominal disease without peritoneal disease includes (i.e., liver metastases without peritoneal disease): peritoneal attachment of the hepatic left lateral segment and the spleen, 2 cm along the incision at the anterior abdominal wall and the falciform ligament (Appendix 1).

3.2.7. Para-aortic lymph-node metastases:

- To be considered eligible for CHPP and debulking with “positive” para-aortic lymph nodes, patients will have no evidence of metastatic disease outside of para-aortic lymph nodes on preoperative imaging and no evidence of hepatic or peritoneal metastases on intraoperative examination.
- Stations 16a1 and/ or b2 will be resected when technically possible.

3.2.8. Lung metastases:

- Timing of resection will be in the best interest of each individual patient. The decision will be made by the thoracic surgeon and the GI surgeon. It can either be performed at the same time as the gastric resection or at a later time point, with a delay of no more than 16 weeks in cases of synchronous disease. **Note:** patients must begin chemotherapy within 24 weeks of randomization.
- Lung metastasectomy will follow the standard of care and as defined by the inclusion/exclusion criteria.

